### **5.6.3 Withdrawal of informed consent**

Patients themselves or parents/ legal guardians may voluntarily withdraw consent for their child to participate in the study for any reason at any time. Withdrawal of consent from the study is defined as when a patient does not want to or the patient's parent/ legal guardian does not want their child to:

- Participate in the study anymore  
and
- Does not want any further visits or assessments  
and

- Does not want any further study related contacts and
- Does not allow analysis of already obtained biologic material

In this situation, the investigator must make every effort (e.g. telephone, e-mail, letter) to determine the primary reason for the patient's or parent's/ legal guardian's decision to withdraw their consent and record this information.

Study treatment must be discontinued and no further assessments conducted, and the data that would have been collected at subsequent visits will be considered missing.

Further attempts to contact the parent/legal guardian are not allowed unless safety findings require communicating or Follow-up.

All efforts should be made to complete the assessments prior to study withdrawal. A final evaluation at the time of the patient's study withdrawal should be made as detailed in [Table 6-1](#).

#### **5.6.4 Lost to Follow-up**

For subjects whose status is unclear because they fail to appear for study visits without stating an intention to discontinue or withdraw, the investigator should show "due diligence" by documenting in the source documents steps taken to contact the subject, e.g. dates of telephone calls, registered letters, etc. If contact has not been re-established, all efforts should still be made to locate the patient and obtain information regarding concomitant medications, serious adverse events, and survival status at the end of the 2 weeks intended treatment epoch (Visit 299). This information should also be obtained at the safety Follow-up visit (Visit 301). A patient cannot be considered as lost to Follow-up until the time point of his/her scheduled end of study visit has passed.

#### **5.6.5 Early study termination by the sponsor**

The study can be terminated by Novartis at any time for any reason. This may include reasons related to the benefit risk assessment of participating in the study, practical reasons, or for regulatory or medical reasons (including slow enrolment). Should this be necessary, the patient must be seen as soon as possible and treated as a prematurely withdrawn patient. The investigator may be informed of additional procedures to be followed in order to ensure that adequate consideration is given to the protection of the patient's interests. The investigator will be responsible for informing the Institutional Review Board/Independent Ethics Committee (IRBs/IECs) of the early termination of the trial.

## **6 Visit schedule and assessments**

The study will consist of a Screening epoch, a Run-in epoch, a 2-week blinded treatment epoch and a Follow-up epoch of 30 days after the last treatment.

[Table 6-1](#) lists all the assessments to be performed for the study and indicates with an "X" the visits at which they will be performed. Patients should be seen for all visits on the designated day or as close as possible to that date. All data obtained for these assessments must be supported in the patients' source documentation.

Study assessments should be performed in a manner that the spirometry measurements occur at the scheduled time point (See [Table 6-2](#) and [6-3](#) for Timed Assessments).

Whenever other assessments are scheduled at the same time-point, spirometry should occur at the scheduled time point or as near as possible.

Patients must be seen for all visits on the designated day, or as close to it as possible. Visit 199/201 (Randomization) and 299 (End of treatment) must occur in the morning, since patients will be taking their study medication in the morning. Missed or rescheduled visits should not lead to automatic discontinuation. Patients who prematurely discontinue the study for any reason should be scheduled for a visit as soon as possible, at which time assessments listed for early discontinuation will be performed.

**Since the first spirometry measurement is 45 minutes prior to inhalation of study medication, and study medication is administered in the morning, it is important to schedule study visits early enough so the patient will have enough time to take their fluticasone on site, have other study assessments done (questionnaire, vital signs, ECG, labs), have the first spirometry 45 minutes prior to study medication, and be dosed with study medication in the morning.**

Patients who discontinue early are not required to undergo the spirometry measurements. However, at least one spirometry measurement should be measured if the patient can tolerate it. Study drug is not administered following early discontinuations.

If a patient's parent/legal guardian refuses to bring their child to the clinic for a discontinuation visit, or is unable to do so, every effort should be made to contact the parent/legal guardian, by telephone, to determine the reason for their child's study discontinuation.

Study medication should be reconciled and the adverse event and concomitant medications reconciled on the CRF. Patients must return the indacaterol at the end of the study.

Thirty days after the End of treatment epoch (Visit 299), the patient's parent/ legal guardian will be contacted for safety evaluations following the last administration of study treatment. This information should be captured in the patient's source documents and SAEs/ AEs will be captured in the eCRF (Visit 301).

**Table 6-1 Assessment schedule**

Epoch	Screening*	Run-in		Treatment		Follow-up
					End of study treatment/ Early termination**	
Visit	1	101	199	201	299	301 
Day Note: V199 and 201 will occur on the same day if the patient is randomized.	Up to 30 days prior to Visit 101	-14	1	1	14	44
Obtain parental Informed Consent / patient assent (if applicable)	X					
Current medication review/ adjust	X					
Contact IRT	S	S	S	S	S**	S**
Randomization via IRT				S		
Inclusion/Exclusion criteria	X	X	X			
Demographics, Medical History	X					
Pulmonary history: - protocol solicited events for asthma	X					
Asthma exacerbation history	X					
Smoking exposure	X					
Prior/ concomitant medication review	X	X	X	X	X**	
Urine pregnancy test  (if applicable)	X	X	X		X**	

Epoch	Screening*	Run-in		Treatment		Follow-up
					End of study treatment/ Early termination**	
Visit	1	101	199	201	299	301 
Day Note: V199 and 201 will occur on the same day if the patient is randomized.	Up to 30 days prior to Visit 101	-14	1	1	14	44
Evaluation of sexual development status 	X					
Device training 	S	S	S			
Height and weight		X	X		X**	
Physical examination complete		S				
Physical examination short			S		S**	
Oropharyngeal examination		S	S		S**	
ECG 		X	X	X	X**	
Vital signs 		X	X	X	X**	
Issue rescue medication as necessary	S	S	S	S		
Review rescue medication use		X	X	X	X**	
Issue fluticasone propionate	X					
Review daily fluticasone use		X	X	X	X**	
Spirometry Practice	S					

Epoch	Screening*	Run-in		Treatment		Follow-up
					End of study treatment/ Early termination**	
Visit	1	101	199	201	299	301 
Day Note: V199 and 201 will occur on the same day if the patient is randomized.	Up to 30 days prior to Visit 101	-14	1	1	14	44
(Optional)						
Screening spirometry (FEV 1 ) 		X	X			
Screening reversibility (SABA) 		X				
Spirometry 			X	X	X**	
Issue e-Diary	S					
Issue Peak Flow meter	S					
Review and upload e-Diary recordings		S	S	S	S**	
Dispense study medication via IRT				S		
Administer study drug at visit				X	X	
Provide parent/ legal guardian and patient with instructions to record time of last dose of study medication taken on Day 13 (or one day prior to Visit 299/Day 14).				S		

Epoch	Screening*	Run-in		Treatment		Follow-up
					End of study treatment/ Early termination**	
Visit	1	101	199	201	299	301 
Day Note: V199 and 201 will occur on the same day if the patient is randomized.	Up to 30 days prior to Visit 101	-14	1	1	14	44
Record time of study drug taken one day prior (Day 13) to Visit 299/Day 14					X**	
Collect unused study medication					S**	
Record interruption/ changes in study drug administration to assess compliance				X	X**	
AE recording		X	X	X	X**	X
SAE recording	X	X	X	X	X**	X
Review and record surgeries and procedures		X	X	X	X**	X
Study disposition (Screening)	X					
Study disposition (Run-in)			X			
Study disposition (End of Treatment)					X**	
Study disposition (Follow-up)						X
Safety Lab assessments 		X	X		X**	

Epoch	Screening*	Run-in		Treatment		Follow-up
					End of study treatment/ Early termination**	
Visit	1	101	199	201	299	301 
Day Note: V199 and 201 will occur on the same day if the patient is randomized.	Up to 30 days prior to Visit 101	-14	1	1	14	44
(hematology, chemistry, urine dipstick)						
PK sampling 			X	X	X**	
ACQ-IA 		X	X		X**	
Telephone parent/ legal guardian in advance of study visit, with reminder to not take rescue medication within 6 hours of study visit, and bring in all study medication and e-Diary		S	S	S	S	

\*Screening Visit 1 and Run-in Visit 101 can occur on the same day if patient did not take any salbutamol/albuterol within 6 hours of the study visit.

\*\*These assessments should be conducted for patients who discontinue.

S These assessments are source documentation only and will not be entered into the CRF.

X Assessment to be reported in the clinical database.

For females of child-bearing potential only.

Labs and urine dipstick are done pre-dose.

Details of timed assessments are provided in [Table 6-2](#) and [6-3](#).

Device training at Visit 1 is for e-diary/peak flow meter, salbutamol/albuterol and fluticasone propionate inhaler. Device training at Visits 101 and 199 is for Concept1.

The ACQ-IA is completed at the clinic, before any other assessment.

Information about any AEs/ SAEs occurring within 30 days of the patients' last study treatment will be obtained by a telephone call 30 days after the patient's last dose of study drug for completed patients. For patients who withdraw early, please refer to discontinuation of study treatment and premature patient withdrawal Section.

Epoch	Screening*	Run-in		Treatment		Follow-up
					End of study treatment/ Early termination**	
Visit	1	101	199	201	299	301 
Day Note: V199 and 201 will occur on the same day if the patient is randomized.	Up to 30 days prior to Visit 101	-14	1	1	14	44

**Table 6-2 Timed assessment schedule (Visit 199)**

	Time point vs. 0 (dose time)***	ACQ-IA	ECG	Vitals (Systolic/diastolic BP /radial pulse)	PK	Hematology/chemistry/urine dipstick	Spirometry	Call IRT**
Visit 199	≤ - 2 hr	Administer fluticasone dose and ancillary study assessments						
	≤ - 2 hr	X	X	X	X	X		
	-45 min						X*	X
	-15 min						X	

\*At Visit 199, patients are required to meet FEV1 criteria of ≥50% and ≤ 90% of the predicted normal value for the patient. If criteria are met at this visit, the patient will be immediately randomized.  
\*\*IRT can be called for randomization information after the -45 minute spirometry assessment, assuming the patient meets the FEV1 criteria at -45 min. Study medication should not be dispensed until appropriate time in Visit 201.  
\*\*\*All time points are approximate time points, and fluctuations are allowed.

**Table 6-3 Timing of key visit procedures during treatment**

	Time point vs. 0 (dosing time)***	ACQ-IA	Vitals (Systolic/diastolic BP and radial pulse)	PK	Hematology/chemistry/urine dipstick	ECG	Spirometry	
Visit 201	0 min	Morning dose of study medication						
	15 min		X	X				
	20 min					X		
	30 min						X	
	50 min						X	
	1 hour		X**	X			X	
Visit 299	≤ - 2 hr	Administer fluticasone dose and ancillary study assessments						
	≤ - 2 hr	X*	X	X	X	X**		
	-45 min						X	
	-15 min						X	
	0 min	Morning dose of study medication						
	15 min		X	X				
	20 min					X		
	30 min						X	
	50 min					X**		
	1 hour		X**	X			X	

\*ACQ-IA should be given prior to any other assessment.  
\*\* Vitals done 1 hour post-dose should be taken *before* the 1-hour post-dose spirometry measurement.  
\*\*\* All time points are approximate time points, and fluctuations are allowed.

## **6.1 Information to be collected on screening failures**

All patients/subjects who have signed informed consent but not entered into the next epoch will have the study completion page for the Screening epoch, demographics, inclusion/exclusion, and serious adverse event (SAE) data collected. Adverse events that are not SAEs will be followed by the investigator and collected only in the source data.

## **6.2 Patient demographics/other baseline characteristics**

Patient demographic and baseline characteristic data to be collected on all patients include:

- Year of birth
- Age (calculated)
- Gender
- Race & Ethnicity
- Height & Weight
- Body Mass Index (BMI) (calculated)
- Baseline physical examination (not databased other than in the context of relevant medical history)
- Vital signs
- ECG
- Date of diagnosis of asthma
- Relevant medical history/current medical condition present before signing the informed consent
- Smoking exposure
- Health status
- Prior/ concomitant medication (asthma and non-asthma related)
- Pre and post-bronchodilator spirometry (Screening spirometry and reversibility testing).

## **6.3 Treatment exposure and compliance**

The time of study treatment dosing, at Visit 201 and 299/End of treatment, will be collected on the e-CRF as well as any dosing interruptions. For assessments where spirometry is performed, the time of dosing is to be taken from the spirometer.

Study treatment compliance should be assessed by the investigator and/or center personnel at all visits. Where necessary, the Investigator will discuss compliance/documentation issues with the patient's parent/legal guardian. The Investigator or designee will collect, from the patient's parent/legal guardian, the used/unused investigational medication and packaging (unused capsules/blister strips SDDPIs) at Visits 299/End of Treatment/ Early Treatment Discontinuation. Study treatment compliance will be assessed from the capsule count from previously dispensed blister strips for the Concept1®.

The number of puffs of rescue medication (salbutamol/albuterol) between study visits will be recorded by the patient's parent/ legal guardian in the e-Diary.

Fluticasone use should be assessed by the investigator and/or center personnel at all visits. The investigator or designee should ask the patient and parent about their daily fluticasone use and should document this in the patient's source document as well as in the eCRF.

## **6.4 Efficacy**

The following assessments of efficacy will be performed:

- Spirometry
- Pediatric ACQ-IA
- Asthma symptoms recorded in e-Diary
- Peak Expiratory Flow
- Rescue Medication Use

### **6.4.1 Spirometry assessments**

The following spirometry assessments will be made:

- Forced expiratory volume in 1 second (FEV1)
- Forced Vital Capacity (FVC)
- Spirometric assessments will be measured at Visits 199, 201 and 299/EOT as indicated in [Table 6-1](#) through [Table 6-3](#).
- Pre-dose FEV1 is defined as the mean of the two FEV1 values measures at -45 min and -15 min prior to morning dose.

Please refer to the Spirometry Guidance in [Appendix 3](#) and [Table 6-2](#) and [Table 6-3](#) for full details on scheduling and performing spirometry.

### **6.4.2 Patient reported outcomes (PRO)**

#### **Asthma Control Questionnaire-Interviewer administered, for children**

In this study, the Asthma Control Questionnaire Interviewer - Administered (ACQ-IA) will be used to assess improvements in asthma symptom control. The ACQ-IA is a seven-item disease-specific instrument developed and validated to assess asthma control in patients in clinical trials as well as in individuals in clinical practice. The ACQ is valid for use in children 6-16 years old, and has strong measurement properties in this age group. Initial cognitive debriefing studies provided evidence that children 11 years and older could understand the instructions, questions and response options of the self-administered version of the adult ACQ accurately and unaided; however, children 10 years and younger needed help. Therefore, the interviewer-administered version of the adult ACQ was developed for children 6-10 years old, and must be administered by a trained interviewer ([Juniper et al 2010](#)). Given the fact that this trial includes 11-year-old, and to make it consistent, all patients will have the ACQ given to them by a trained interviewer.

The ACQ-IA will be provided to the site. All seven items are then scored on a 7-point Likert scale, with 0 indicating total control and 6 indicating no control. The questions are equally weighted and the total score is the mean of the seven items.

The interviewer must ask the child the first 6 questions of the ACQ-IA and the child should be encouraged to respond directly (parent/ legal guardians should only help if the child is having

difficulties responding). The investigator should complete the last question (for the last ACQ question – airway caliber FEV1% predicted based on the masterscope at site) at the investigator's site at Visits 101, 199, and 299/End of treatment (EOT).

The ACQ-IA will be asked in the language most familiar to the patient, at the scheduled study visit prior to the patient seeing the investigator for any clinical assessment or evaluation. The patient's parent/ legal guardian can be present during the interview. The interviewer should make the child comfortable and should reassure the child that there are no right or wrong answers. The interviewer can have the child read aloud each of the questions and responses, if the child is able to read. The interviewer will complete the questionnaire with the patient's responses. All questionnaires should be complete.

For paper CRFs the original questionnaire will be kept with the patient's file as the source document.

Completed questionnaires will be reviewed and examined by the investigator, before the clinical examination, for responses that may indicate potential adverse events (AEs) or serious adverse events (SAEs). The investigator should review not only the responses to the questions in the questionnaires but also for any unsolicited comments written by the patient. If AEs or SAEs are confirmed, then the physician must record the events as per instructions given in [Section 7.1](#) and [Section 7.2](#) of the protocol.

#### **6.4.3 Electronic Diary**

At Visit 1, parents/ legal guardians will be provided with an e-Diary to record their child's rescue medication (salbutamol/albuterol) use. From Visit 101 on, they will record their child's clinical symptoms and PEF in the e-diary. The patient's parent/ legal guardian will be instructed to routinely complete the e-Diary twice daily – at the same time each morning and again approximately 12 hours later in the evening. The e-Diary is to be reviewed at each clinic visit until study completion. Sites and the patient's parent/ legal guardian will receive appropriate training and guidance on the use of the e-Diary device. A list of the Patient asthma control e-Diary questions is provided in [Appendix 4](#).

#### **6.4.4 Peak expiratory flow**

An electronic Peak Flow Meter part of the e-Diary device will be provided to the patient's parent/ guardian at Visit 1 for the measurement of morning and evening PEF during the study ([Appendix 4](#)).

PEF will be measured at consistent times for a patient, in the morning and evening each day during the study from Visit 1 to 299/End of study. PEF will be measured twice a day; in the morning just prior to taking study medication and again 12 hours later. Patients should be encouraged to perform morning and evening PEF measurements BEFORE taking study medication. At each time point, the parent/guardian should instruct their child to perform 3 consecutive maneuvers within 10 minutes. These PEF values are captured in the e-PEF/diary. The best of 3 values will be used. The PEF/ e-Diary is to be reviewed at each clinic visit until study completion.

#### **6.4.5 Rescue medication usage**

The use of rescue salbutamol/albuterol should be recorded by the patient's parent/ legal guardian in the e-Diary twice each day in the morning and evening. In the morning the

number of puffs of rescue medication their child has taken during the night and since the last diary entry, and in the evening the number of puffs of rescue medication the child has taken during the day since the morning diary entry should be recorded.

#### **6.4.6 Appropriateness of efficacy assessments**

The efficacy assessments selected are standard for this indication/patient population.

### **6.5 Safety**

The following safety assessments will be performed:

- Medical history and physical examination including oropharyngeal examination
- Vital signs
- Hematology, blood chemistry, urine dipsticks
- ECG
- Adverse events including asthma exacerbations, worsening asthma, and serious adverse events

ECG and Laboratory assessments, excluding urine dipsticks, will be centralized.

#### **6.5.1 Physical examination**

A complete physical examination will include the examination of general appearance, skin, neck (including thyroid), eyes, ears, nose, throat, lungs, heart, abdomen, back, lymph nodes, and extremities, vascular and neurological. An oropharyngeal examination will be performed at each clinic visit. A short physical examination will include the examination of vital signs, heart, lungs, abdomen, extremities and any other evaluation the Investigator considers appropriate based on the patient's clinical status at the time of the visit.

Information for all physical examinations must be included in the source documentation at the study site. Significant findings that are present prior to informed consent being granted must be included in the Relevant Medical History/Current Medical Conditions screen on the patient's e-CRF. Significant findings made after informed consent (Visit 1) is given which meet the definition of an Adverse Event must be recorded on the Adverse Event screen of the patient's e-CRF.

#### **6.5.2 Vital signs**

Systolic and diastolic blood pressure and radial pulse rate (over a 30 sec interval), performed in the sitting position, will be recorded at each scheduled clinic visit as detailed in [Table 6-1](#) through [Table 6-3](#). Vitals are taken pre-dose and 15 minutes and 1 hour post-dose. The vitals taken 1-hour post-dose should be done *before* the 1-hour post-dose spirometry measurement.

#### **6.5.3 Height and weight**

Height in centimeters (cm) and weight (to the nearest 0.1 kilogram [kg] in indoor clothing, but without shoes) will be measured at Visit 101, 199, and 299. BMI will be calculated based on height and weight.

## 6.5.4 Laboratory evaluations

A central laboratory will be used for analysis of all specimens collected. Details on the collections, shipment of samples and reporting of results by the central laboratory are provided to investigators in the laboratory manual.

All patients with laboratory tests containing clinically significant abnormalities should be followed regularly until the values return to within the normal ranges or until a valid reason other than drug-related adverse experiences is identified, even after the medication has discontinued.

Safety Laboratory assessments (hematology, clinical chemistry, blood eosinophil counts) will be performed at Visits 101, 199 and 299/EOT if applicable.

### 6.5.4.1 Hematology

Hemoglobin, hematocrit, red blood cell count, white blood cell count with differential, and platelet count will be measured.

Peripheral blood eosinophil counts will be captured with a unit of cells/ mcL.

### 6.5.4.2 Clinical chemistry

Albumin, alkaline phosphatase, aspartate aminotransferase (AST) or Serum Glutamic-Oxaloacetic Transaminase (SGOT), alanine aminotransferase (ALT) or Serum Glutamic Pyruvic Transaminase (SGPT), bilirubin, creatinine,  $\gamma$ -GT, glucose, potassium, magnesium, BUN and uric acid will be measured.

If the total bilirubin concentration is increased above 1.5 times the upper limit of normal range, total bilirubin should be differentiated into the direct and indirect reacting bilirubin.

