## **7.3 Liver safety monitoring**

To ensure patient safety and enhance reliability in determining the hepatotoxic potential of an investigational drug, a standardized process for identification, monitoring and evaluation of liver events has to be followed.

The following two categories of abnormalities / adverse events have to be considered during the course of the study (irrespective of whether classified/reported as (S)AE):

- Liver laboratory triggers, which will require repeated assessments of the abnormal laboratory parameter
- Liver events, which will require close observation, Follow-up monitoring and completion of the standard base liver CRF pages

Please refer to [Table 13-1 in Appendix 7](#) for complete definitions of liver laboratory triggers and liver events.

Every liver laboratory trigger or liver event as defined in [Table 13-1 of Appendix 7](#) should be followed up by the investigator or designated personal at the trial site as summarized below. Detailed information is outlined in [Table 13-2 in Appendix 7](#).

For the liver laboratory trigger:

- Repeating the liver function test (LFT) within the next week to confirm elevation.

These LFT repeats must be performed using the central laboratory if possible. If this is not possible, then the repeats can be performed at a local laboratory to monitor the safety of the patient. Repeats laboratory must then be performed at central laboratory as soon as possible. If a liver event is subsequently reported, any local LFTs previously conducted that are associated with this event must be reported on the Liver CRF pages.

- If the elevation is confirmed, close observation of the patient will be initiated, including consideration of treatment interruption if deemed appropriate.

For the liver events:

- Repeating the LFT to confirm elevation as appropriate
- Discontinuation of the investigational drug if appropriate
- Hospitalization of the patient if appropriate
- A causality assessment of the liver event via exclusion of alternative causes (e.g., disease, co-medications)
- An investigation of the liver event which needs to be followed until resolution.

These investigations can include serology tests, imaging and pathology assessments, hepatologist's consultancy, based on investigator's discretion. All Follow-up information, and the procedures performed must be recorded on appropriate CRF pages, including the liver event overview CRF pages.

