**Table 13-2 Follow Up Requirements for Liver Events and Laboratory Triggers**

Criteria	Actions required	Follow-up monitoring
Potential Hy's Law case a	
 
• Discontinue the study treatment immediately
 
• Hospitalize, if clinically appropriate
 
• Establish causality
 
• Complete liver CRF
 
	ALT, AST, TBL, Alb, PT/INR, ALP and γGT until resolution c (frequency at investigator discretion)
ALT or AST		
$> 8 \times \text{ULN}$	
 
• Discontinue the study treatment immediately
 
• Hospitalize if clinically appropriate
 
• Establish causality
 
• Complete liver CRF
 
	ALT, AST, TBL, Alb, PT/INR, ALP and γGT until resolution c (frequency at investigator discretion)
$> 3 \times \text{ULN}$ and INR $> 1.5$	
 
• Discontinue the study treatment immediately
 
• Hospitalize, if clinically appropriate
 
• Establish causality
 
• Complete liver CRF
 
	ALT, AST, TBL, Alb, PT/INR, ALP and γGT until resolution c (frequency at investigator discretion)
$> 5 \text{ to } \leq 8 \times \text{ULN}$	
 
• Repeat LFT within 48 hours
 
• If elevation persists, continue Follow-up monitoring
 
• If elevation persists for more than 2 weeks, discontinue the study drug
 
• Establish causality
 
• Complete liver CRF
 
	ALT, AST, TBL, Alb, PT/INR, ALP and γGT until resolution c (frequency at investigator discretion)

Criteria	Actions required	Follow-up monitoring
> 3 × ULN accompanied by symptoms b	
 
Discontinue the study treatment immediately
 
Hospitalize if clinically appropriate
 
Establish causality
 
Complete liver CRF
 
	ALT, AST, TBL, Alb, PT/INR, ALP and γGT until resolution c (frequency at investigator discretion)
> 3 to ≤ 5 × ULN (patient is asymptomatic)	
 
Repeat LFT within the next week
 
If elevation is confirmed, initiate close observation of the patient
 
	Investigator discretion Monitor LFT within 1 to 4 weeks
ALP (isolated)		

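### A liver event is defined by INR > 1.5, but in symptom-free children with ALT or AST at > 3 to ≤ 5 × ULN no protocol-required test yields an INR

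*Protocol*

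**What the plan says.** Table 13-1 (Appendix 7) lists ALT or AST above 3 × ULN with INR above 1.5 as a liver event. Table 13-2 attaches immediate discontinuation, a causality assessment and the liver CRF to it.

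The tests to be run are listed in section 6.5.4. For hematology (6.5.4.1): "Hemoglobin, hematocrit, red blood cell count, white blood cell count with differential, and platelet count will be measured". The chemistry list (6.5.4.2) covers albumin, ALP, AST, ALT, bilirubin, creatinine and γ-GT, and ends with "glucose, potassium, magnesium, BUN and uric acid will be measured". Neither names PT or INR. According to 6.5.4, these assessments "will be performed at Visits 101, 199 and 299/EOT if applicable".

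When ALT or AST first rises to > 3 to ≤ 5 × ULN in a child without symptoms, section 7.3 asks for "Repeating the liver function test (LFT) within the next week to confirm elevation". The matching row of Table 13-2 asks for "Repeat LFT within the next week", then close observation if the rise is confirmed. Its follow-up column reads "Investigator discretion Monitor LFT within 1 to 4 weeks". PT/INR is requested only in the follow-up column of other rows: "ALT, AST, TBL, Alb, PT/INR, ALP and γGT until resolution".

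Section 5.6.2 separately requires study treatment to be discontinued for clinically significant laboratory abnormalities. It gives an LFT above 3 × ULN as an example, with no INR condition.

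**The concern.** A definition that rests on a laboratory value works only if the value is obtained when the definition has to be applied. Here one liver event depends on INR, while in the group where that event is most relevant the protocol asks only for a repeat LFT.

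A symptom-free child at > 3 to ≤ 5 × ULN with impaired clotting would, if the text is followed as written, be handled as a laboratory trigger. Under Table 13-1 the same child is a liver event. By 7.3 that means liver CRF pages and follow-up to resolution, and by 6.5.4.4 SAE reporting if the event counts as medically significant. Two children with the same biology could therefore be classified differently according to whether a site chose to order a clotting test.

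**Working it through.** The plan states no figure to reproduce on this point, so the check sets the sections side by side.

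**1. Laboratory quantities in the Table 13-1 definitions, and where each is ordered**
- ALT, AST, ALP and total bilirubin: in the chemistry list, 6.5.4.2.
- Conjugated bilirubin fraction (used in the Hy's Law definition): ordered conditionally in 6.5.4.2, once total bilirubin exceeds 1.5 × ULN.
- Eosinophils (used in the symptom criterion): in 6.5.4.1.
- INR: in neither list, and with no conditional order of the kind written for bilirubin.

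INR is therefore the only laboratory quantity that helps define a liver event but is not ordered for that purpose.

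**2. Table 13-2, row by row**
- PT/INR appears in the follow-up column of 7 of the 11 rows: potential Hy's Law; ALT/AST > 8 × ULN; > 3 × ULN with INR > 1.5; > 5 to ≤ 8 × ULN; > 3 × ULN with symptoms; isolated bilirubin > 2 × ULN; jaundice.
- It is absent from 4: ALT/AST > 3 to ≤ 5 × ULN without symptoms; isolated ALP > 2 × ULN; bilirubin > 1.5 to ≤ 2 × ULN; any adverse event suggesting liver toxicity.
- Of the 7, one already presupposes that INR is known to exceed 1.5. The other 6 are reached on other grounds, which already make the child a liver event.

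**3. Where the INR criterion adds to classification**
- ALT/AST > 5 × ULN: already a liver event.
- > 3 to ≤ 5 × ULN with the listed symptoms, jaundice, or bilirubin or ALP above its own event limit: already a liver event.
- > 3 to ≤ 5 × ULN with none of these: INR alone decides between laboratory trigger and liver event. The required test here is the repeat LFT, and neither 7.3 nor Table 13-2 names INR.

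**4. Where the INR criterion adds to stopping**
- At > 5 to ≤ 8 × ULN, Table 13-2 asks for a repeat within 48 hours and discontinuation if the elevation lasts more than 2 weeks. The INR row says immediately. PT/INR is part of follow-up in this band, so the criterion can operate there.
- At > 3 to ≤ 5 × ULN without symptoms, Table 13-2 says repeat and observe, while 5.6.2 gives LFT above 3 × ULN as an example of a mandatory stop. These two do not agree, whatever the INR.

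**5. Timing**
- Safety samples are scheduled at Visits 101, 199 and 299. The first two precede the first dose. By Table 6-3 the third is drawn before the last supervised dose, on Day 14.
- Visit 299 is thus the only scheduled sample after dosing starts. A result that could change dosing would come from the Visit 199 sample, if reported after randomization, or from an unscheduled test.

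**6. Size**
- The documents give no rate of ALT/AST above 3 × ULN. Assume 0.5% to 2% of the 80 randomized children.
- 80 × 0.005 = 0.4 and 80 × 0.02 = 1.6 children.
- The affected group is smaller still: it must also be at ≤ 5 × ULN, symptom-free, without another liver-event criterion, and have INR above 1.5. The documents do not allow that fraction to be estimated.

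**The case against.** Much of the opposing case stands.

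- INR can be obtained. Follow-up in the symptom-free row is at the investigator's discretion, 7.3 calls for close observation once the rise is confirmed, and section 11 allows extra safety assessments case by case.
- The content of an LFT is not defined and the laboratory manual is not shown, so a repeat LFT that includes INR cannot be excluded. Against this, the analyte lists are in the protocol itself and omit it.
- Absence from the routine panel is not in itself a contradiction. Appendix 7 also calls for hemolysis tests outside the panel. But those are named in a row already reached on bilirubin and define no event, whereas INR defines one.
- Stopping is largely covered by 5.6.2, and 6.5.4 already requires clinically significant abnormalities to be followed.
- No planned analysis is affected. Section 9.5.2 plans summaries of adverse events and laboratory abnormalities, not a count by Table 13-1 criterion.

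A reader might infer that the INR criterion can never be met, that a reported count would be zero by construction, or that > 3 to ≤ 5 × ULN is the only band where INR matters. The documents support none of these. INR may be ordered at discretion, no such count is planned, and INR also changes the stopping action at > 5 to ≤ 8 × ULN.

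What remains is that, in one defined group, detection of a liver event is left to chance ordering.

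**Conclusion.** The point holds in a limited form. In symptom-free children at > 3 to ≤ 5 × ULN with no other liver-event criterion, no test that the protocol expressly requires would detect the INR-defined liver event. This rests on reading LFT as the liver analytes in 6.5.4.2.

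The consequence is mainly for classification, the liver CRF and possible SAE reporting, in a group likely to number at most one or two children and quite possibly none. The effect on stopping is small, given 5.6.2 and a single scheduled sample after dosing starts, on the last dosing day. The primary endpoint and the dose-selection evidence are untouched.

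The check also shows a plainer inconsistency: at > 3 × ULN, 5.6.2 points to mandatory discontinuation, while the symptom-free row of Table 13-2 points to repeat and observe. The two could be read together only if the phrase on clinical significance in 5.6.2 is taken to exempt such children, and the protocol does not say so.

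This is a minor but safety-relevant repair.

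**What to change.** Reconcile 5.6.2, 6.5.4.1, 6.5.4.2, 7.3 and Tables 13-1 and 13-2 on two matters:

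- Every test that defines a liver event should either be obtained when the definition has to be applied or not be used in the definition.
- The action at ALT or AST above 3 × ULN should be the same wherever it is stated.

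Which resolution to adopt, and what clinical action follows, is for the sponsor's clinical team; this review takes no position on either.

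The cost is a short text change, with a matching line in the laboratory manual if needed. If the INR test is kept, it adds at most one tube to a repeat draw that is already planned, in very few children.
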